5.3.2.2. Other Patient Reported Outcome

Time to return to daily activities

Time to return to daily activities will be analyzed by Kaplan-Meier analysis, Gehan-Wilcoxon test, log-rank test, AFT model, and Cox proportional hazards model.

The AFT and Cox models will include the fixed categorical effects for treatment (with placebo as the reference) and stratification factors.

Patient global Impression parameters and daily activities resumption

The subject's perception of severity and change of influenza symptoms (PGIS and PGIC) and the daily activities resumption will be tabulated per parameter and per category by analysis timepoint using frequency tabulations.

EQ-5D dimensions

Tabulations of the number (and percentage) of subjects per parameter, response and timepoint will be shown per treatment group.

EQ-5D VAS, EQ-5D Valuation index

The actual values and changes from baseline will be shown descriptively and by mean (SE) plots per analysis visit.

The proportion of subjects with a clinically relevant change from baseline of 7 or more (decrease or increase) and of 10 or more (decrease or increase) will be provided for each post-baseline assessment.

Missing data

1. If – for a questionnaire – one (or more) dimensions of the descriptive system are missing then
 - The EQ-5D VAS will be included in the analysis
 - The valuation index will not be included in the analysis
 - The non-missing dimensions of EQ-5D descriptive system will be included in the analysis of the separate dimensions
2. If – for a questionnaire – the EQ-5D VAS is missing then
 - the EQ-5D descriptive system and valuation index will be included in the analysis if complete (otherwise see 1)

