  - n. The results of an earlier sample collected and tested positive for influenza A infection after the onset of symptoms, using a RIDT or, if available, a PCR-based or other rapid molecular diagnostic assay, can be used in lieu of the local virology testing at screening. This sample is used to determine eligibility.
  - o. Central virology testing: Nasal MT swabs should be obtained from the left and the right nostrils and pooled into the same collection tube. The samples will be collected at screening/baseline and on Days 3, 6, 10, and 14. The screening/baseline sample needs to be collected predose, as close as possible, to the first dose. Sampling should be done at approximately the same time ( $\pm 4$  hours) on each sampling day. Leftovers from nasal MT swabs collected for virology testing may be used for protein biomarker analysis.
  - p. At the time points where both nasal MT swabs and pharmacokinetic (PK) samples are obtained, these samples should be obtained as close together in time as possible.
  - q. Vital signs include body temperature, pulse rate, respiratory rate, and blood pressure.
  - r. The Flu-iiQTM questionnaire will be completed twice daily throughout the study; it will be programmed onto the electronic PRO (ePRO) device.
  - s. Questionnaire (Return to daily activities) to be completed at screening/baseline (as close as possible to first study drug intake) and then once daily onto the ePRO device.
  - t. Questionnaire PGIS to be completed from screening/baseline (as close as possible to the first study drug intake) and then once daily throughout Final Study Visit/Safety Follow-up Visit.
  - u. Questionnaire EQ-5D to be completed at screening/baseline (as close as possible to the first study drug intake); Questionnaires EQ-5D and PGIC to be completed on Day 6, 14, and 28 onto the ePRO device.
  - v. Follicle-stimulating hormone (FSH) will be tested at screening for female subjects who are amenorrheic for 12 months or less.
  - w. If feasible, safety blood samples will be collected after fasting for at least 10 hours.
  - x. The pharmacogenomic sample should preferably be collected at the specified time point, however if necessary it may be collected at a later time point without constituting a protocol deviation.
  - y. Sparse PK sampling will be performed as follows (if practically feasible):
    - On Day 3: at any time during the visit (date and time of last drug intake before PK sampling will be recorded).

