    - On Day 6: preferentially as close as possible to 12h after the last dose of study drug (ie, the evening dose on Day 5). If treatment was started in the evening of Day 1, PK sampling will be performed on Day 6 before the last drug intake. The date and time of the evening drug intake on Day 5 will be recorded. In case the Day 6 visit is performed on Day 7 (footnote d), the PK sample should be taken as early as possible during the visit (date and time of the last study drug intake before PK sampling will be recorded). Leftovers from samples collected for PK testing may be used for protein biomarker analysis.
  - z. The taste and swallowability questionnaire should only be completed by adolescent subjects for pimodivir or placebo. The questionnaire should be completed within approximately 15 minutes after the first and last intake of the pimodivir or placebo tablet. For subjects who receive the last dose of pimodivir or placebo on Day 6 (see footnote l), the questionnaire should be completed on Day 6.

- aa. In case of antipyretic use, temperature should be taken whenever possible at least 4 hours after antipyretic medication. Temperature at baseline should be measured after randomization and ePRO completion, but before the first dose. Oral temperature will be measured and recorded in the ePRO device by the subject twice daily until Day 14 by all subjects at sites where appropriate forms and translations are available and approved
- bb. PRO completion compliance should be assessed daily by the site staff via the ePRO web platform. Reasons for missing assessment should be documented on the web platform by the site after discussion with the subject.
- cc. PRO assessments will be completed by all subjects at sites where appropriate PROs and translations are available and approved.
- dd. Assessment of inclusion criterion n°2 (flu symptoms severity) must be performed through the evaluation of the subject's answers to Pre-existing Symptom Questionnaire and Flu-iiQ™ Module 1 questions programmed on the ePRO device (before randomization).

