### ***Primary Endpoint***

Time to resolution of the 7 primary influenza-related symptoms is defined as the time from initiation of study treatment to when all symptoms are considered resolved for at least 24 hours. A symptom is considered resolved, depending on pre-existence of the symptom:

- The symptom is pre-existing:
  - The symptom is considered resolved if post-baseline severity is equal or lower than the pre-existing severity
- The symptom is not pre-existing:
  - The symptom is considered resolved if its severity is scored at most mild post-baseline

The primary efficacy analysis of the time to resolution of the 7 primary influenza-related symptoms (cough, sore throat, headache, nasal congestion, feeling feverish, body aches and pains, fatigue) will consist of a stratified Gehan-Wilcoxon test (using the randomization stratification factors, ie, type of baseline SOC and time since onset of symptoms as strata). Kaplan-Meier curves, overall and by stratum, and a stratified log-rank test for time to symptom resolution will also be provided. Additionally, the data will be analyzed using an accelerated failure time model. Also, a Cox proportional hazards model will be applied. Both models will be adjusted for stratification factors and baseline symptom domain score.

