### ***Secondary Endpoints***

The incidence of hospital admissions 28 days after treatment initiation will be analyzed using a logistic regression. Stratification factors will be added as covariates to the model.

Return to daily activities will be assessed once daily by means of the question 'Over the past 24 hours, how much has influenza (flu) interfered with your ability to carry out your daily activities?' The responses will be dichotomized: 'Not at all' and 'A little bit' will be considered as returned to daily activities and 'Somewhat', 'Quite a Bit' and 'Very much' will be considered as not having returned to daily activities. "Time to return to daily activities" is defined as the time from initiation of study treatment to when return to daily activities is reached for at least 24 hours. This endpoint will be analyzed analogously to the primary endpoint.

Time to resolution of fever will be analyzed analogously to the primary endpoint.

The incidence of treatment-emergent adjudicated complications will be analyzed using a logistic regression. Stratification factors will be added as covariates to the model.

The time to viral negativity, by qRT-PCR and viral culture, will be analyzed analogously to the primary endpoint. The viral load over time will be analyzed using mixed effects modeling. Stratification factors will be added as covariates to the model. Additional predictive baseline covariates may be added.

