4.1. Demographics and Baseline Characteristics

Demographics and baseline disease characteristics will also be done on the PP and ITT-ni sets.

Descriptive statistics or frequency tabulation will be provided for the following parameters.

- Demographic parameters:
 - Sex (Male, Female)
 - Race (White, Black or African American, Asian, American Indian or Alaska Native, Native Hawaiian or Other Pacific Islander, Multiple). The specification of the category 'Multiple' will only be listed. The 'Not reported' category will not be added for the denominator.
 - Ethnicity (Hispanic or Latino, Not Hispanic or Latino)
 - Country
 - Geographic region (Based on country according to UN classification of Geographic regions^[5]: Europe/Africa, Northern-America, Latin America and the Caribbean, Asia and Oceania)
 - Age (years and categories: 13-17 years [≥ 13 - < 18], 18-65 years [≥ 18 - ≤ 65], 66-85 years [> 65 - ≤ 85])
 - Age (years and categories: Adolescents (12-17 years) [≥ 12 - ≤ 17], Adults (18-64 years) [≥ 18 - ≤ 64], From 65 to 84 years [≥ 65 - ≤ 84], 85 years and over [≥ 85])
 - Weight at baseline (kg)
 - Height at baseline (cm)
 - BMI at baseline = Weight at baseline (kg) / (Height at baseline (m))² (rounded to 1 decimal. Although available in the raw data, BMI will be recalculated from last weight and height measurement before start of treatment)
 - Current Tobacco use: tobacco, cigarettes, cigars, patches/gum, pipes, E-cigarettes or equivalent, smokeless tobacco (Yes, No, Missing) Note that 'No' also includes ex-smokers
 - Childbearing potential (only listed)

- Baseline disease characteristics:
 - Influenza A subtype category (A/H1N1, A/H3N2, other)
 - Baseline influenza A viral load (log₁₀ vp/mL), assessed by qRT-PCR
 - Baseline influenza A viral titer (log₁₀ TCID₅₀/mL) assessed by viral culture
 - Broad respiratory panel (show the reported pathogen)
 - Baseline composite symptom score of 10 influenza-related symptoms
 - Return to daily activities questionnaire baseline category

- Patient Global Impression of Severity of Influenza symptoms at baseline
- EQ-5D VAS at baseline
- EQ-5D Valuation index at baseline
- Respiration rate at baseline (breaths/min)
- Heart rate (beats/min)
- Temperature (°C) at baseline
- qRT-PCR negativity at baseline
- Viral culture negativity at baseline
- Time since onset of influenza symptoms, as randomized (≤ 48 hours, > 48 hours)

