5.3.2.3. Clinical Outcomes

Incidence of treatment-emergent adjudicated influenza complications, hospital admission rate, incidence of treatment-emergent adjudicated influenza complications including hospital admission, and incidence of all-cause mortality

The number and percentage of subjects in each parameter category and subcategory will be tabulated and listed. All subjects in the applicable analysis set will be counted for the denominator of the proportion.

The occurrence (yes/no) for hospital admission rate, incidence of treatment-emergent adjudicated influenza complications including hospital admission, and incidence of all-cause mortality will be analyzed using logistic regression as described above (Section 5.3.2).

The occurrence (yes/no) of influenza complications will be analyzed using logistic regression as described above, for each of the following categories:

- the overall influenza complications
- the pulmonary complications,
- the extrapulmonary complications
- the pulmonary complications including sinusitis and otitis
- the infectious complications
- the non-infectious complications
- the major complications
- the minor complications

Time to resolution of fever

Time to resolution of fever will be analyzed similarly as time to return to daily activities.

A subgroup analysis will be done based on the subset of subjects with fever at baseline (temperature $\geq 37.0^{\circ}\text{C}$) as recorded as part of the on-site vital signs assessment.

Temperature recordings made by the subject on the ePRO device lower than 34°C or higher than 43°C will not be included in the analysis.

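### Return to daily activities and resolution of fever are the only time-to-event endpoints whose AFT and Cox models have no baseline severity covariate beyond the stratification factors

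*SAP*

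**What the plan says.** Protocol 11.4 describes the primary endpoint's AFT and Cox models with "Both models will be adjusted for stratification factors and baseline symptom domain score", and SAP 5.2.3 repeats this. Under secondary endpoints, Protocol 11.4 says of return to daily activities: "This endpoint will be analyzed analogously to the primary endpoint". For fever it says: "Time to resolution of fever will be analyzed analogously to the primary endpoint".

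SAP 5.3.2.2 sets the model terms for return to daily activities: "The AFT and Cox models will include the fixed categorical effects for treatment (with placebo as the reference) and stratification factors". No further term follows. SAP 5.3.2.3 then states: "Time to resolution of fever will be analyzed similarly as time to return to daily activities".

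The baseline values are available. The Time and Events Schedule has "Questionnaire (Return to daily activities) to be completed at screening/baseline (as close as possible to first study drug intake", and Protocol 9.1.2 places the baseline questionnaires before the first study drug intake. SAP 4.1 lists "Return to daily activities questionnaire baseline category" among the baseline characteristics, together with baseline temperature. On temperature, the schedule says: "Temperature at baseline should be measured after randomization and ePRO completion, but before the first dose".

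**The concern.** How limited or how febrile a subject is at entry plausibly predicts how soon that subject returns to activity or to normal temperature. The endpoint definitions add to this:

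- **Fever.** SAP 5.3.1.3 treats every subject as febrile at baseline, yet inclusion criterion 2 does not require fever. A subject below 37.0°C at entry who takes no antipyretic can meet the definition from the first recordings.
- **Daily activities.** The definition sets no baseline requirement, so a subject who reports only slight interference at entry is already in the returned category.

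Leaving a prognostic baseline value out of an AFT model gives away precision that the collected data could supply. In a Cox model it also moves the hazard ratio toward 1. In addition, the SAP does not follow the analogy that the protocol draws with the primary endpoint, and it gives no reason.

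**Working it through.** **Step 1: model terms side by side.** These are the AFT and Cox covariates besides treatment.

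- Primary endpoint (Protocol 11.4, SAP 5.2.3): stratification factors and baseline symptom domain score.
- The 10 single symptoms, and the version of the primary that considers improvement from baseline (SAP 5.3.2.1): stratification factors and baseline symptom score.
- Viral negativity by qRT-PCR and by culture (SAP 5.3.2.4): stratification factors and baseline viral load or titer.
- Exploratory Flu-iiQ Modules 2, 3 and 4 (SAP 5.4.2.1): analysed like the single symptoms, so the baseline term carries over.
- Return to daily activities (SAP 5.3.2.2): stratification factors only.
- Fever (SAP 5.3.2.3, by reference to daily activities): stratification factors only.

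The omission is therefore confined to two time-to-event endpoints. The SAP amendment history records no decision to make it.

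**Step 2: size for the AFT estimate.** The documents give no figure to reproduce: no variance for these two endpoints and no strength of association with baseline. Let R² be the share of log-time variance that the covariate explains beyond the strata. R² is an assumption, taken here as 0.05 to 0.20. Ignoring censoring, the ratio of adjusted to unadjusted standard error is sqrt(1 − R²).

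- R² = 0.05: sqrt(0.95) = 0.975, a fall of 2.5%.
- R² = 0.10: sqrt(0.90) = 0.949, a fall of 5.1%.
- R² = 0.20: sqrt(0.80) = 0.894, a fall of 10.6%.

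**Step 3: the same on a power scale, for illustration only.** Take 300 per arm (the 600 of Protocol 11.3), two-sided 5%, and a log-time SD of 0.988. That SD is the log-normal scale for symptom resolution in Protocol Table 2, borrowed because nothing is given for these endpoints. The time ratio of 0.80 is also assumed.

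- Unadjusted SE = 0.988 × sqrt(2/300) = 0.0807.
- |log 0.80| / SE = 0.2231 / 0.0807 = 2.77, so power is Φ(2.77 − 1.96) = 0.790.
- Adjusted power is 0.810, 0.830 and 0.871 at R² = 0.05, 0.10 and 0.20.
- At a time ratio of 0.75, the planning effect for the primary endpoint, unadjusted power is 0.946 and adjusted power is 0.955, 0.964 and 0.979.

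**Step 4: what does not move.** Under SAP 5.3.2 all time-to-event variables are also analysed by the stratified Gehan-Wilcoxon test, the stratified log-rank test and Kaplan-Meier estimates. None of these uses a baseline covariate beyond the strata, so none changes.

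**The case against.** The strongest reply is that these models are supportive. Neither endpoint is in the confirmatory hierarchy (Protocol 11.4, SAP 5.1.1), and the stated objective for each is to investigate, not to show superiority. Protocol section 11 offers a general description and leaves the details to the SAP. The SAP keeps the same methods and strata as the primary, so it can be said to honour the analogy in substance. The protocol also does not say which baseline value an activity question or a thermometer reading should carry. For fever, SAP 5.3.2.3 already plans a subgroup restricted to a baseline temperature of at least 37.0°C.

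Most of this stands, and it limits the weight of the point. It does not explain why these two endpoints alone lack a severity term. The fever subgroup also does not adjust the estimate in the full set.

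A reader might infer several stronger things that the documents do not support:

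- **That the models ignore baseline altogether.** They do not: type of SOC and time since symptom onset are themselves baseline variables.
- **That these are the only secondary analyses without a further covariate.** The logistic models for complications, hospital admission and mortality (SAP 5.3.2, 5.3.2.3) also carry only treatment and strata. The contrast holds among time-to-event endpoints only.
- **That the treatment comparison is biased.** Randomization protects it. The Cox shift reflects non-collapsibility: the less-adjusted hazard ratio is a different estimand, not an error.
- **That the trial gains the equivalent of 5-25% more subjects.** That figure, 1/(1 − R²) − 1, rests on the assumed R² and could apply only to the AFT estimate.

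**Conclusion.** The point holds as a matter of consistency and modest precision. The text comparison is firm: among the time-to-event endpoints, only these two lack a baseline severity covariate, and Protocol 11.4 points to including one. The size is not firm. A fall of about 2.5-11% in the AFT standard error depends on an assumed R² of 0.05-0.20 beyond the strata and on ignoring censoring. The Cox hazard ratio would be somewhat attenuated, by an amount that the documents do not allow one to state. No primary or confirmatory conclusion is affected. Calling this a protocol violation would go too far, because the protocol delegates detail to the SAP and does not define how far the analogy extends. The change is still worth making, because the data are already collected.

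**What to change.** In SAP 5.3.2.2 and 5.3.2.3:

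1. Add the baseline symptom domain score to the AFT and Cox models for both endpoints, as the protocol's analogy with the primary implies. Use the SAP 5.2.3 rule for missing values (ITT-i median).
2. Following the pattern of SAP 5.3.2.1 and 5.3.2.4, also add the endpoint's own baseline. For return to activities this is the baseline daily-activities response, stating whether it enters as a category or as a score. For fever it is baseline temperature, stating whether the on-site vital-signs reading or the subject's ePRO reading is used. Give each a missing-value rule.
3. Keep the baseline-fever subgroup as an additional analysis.
4. If adjustment for strata alone is intended, say so and give the reason.

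Settle the covariates before unblinding, so that the choice cannot appear to depend on the results. The cost is a sentence or two per endpoint and the extra model terms, with no new data.

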5.3.2.3. Clinical Outcomes

Incidence of treatment-emergent adjudicated influenza complications, hospital admission rate, incidence of treatment-emergent adjudicated influenza complications including hospital admission, and incidence of all-cause mortality

The number and percentage of subjects in each parameter category and subcategory will be tabulated and listed. All subjects in the applicable analysis set will be counted for the denominator of the proportion.

The occurrence (yes/no) for hospital admission rate, incidence of treatment-emergent adjudicated influenza complications including hospital admission, and incidence of all-cause mortality will be analyzed using logistic regression as described above (Section 5.3.2).

The occurrence (yes/no) of influenza complications will be analyzed using logistic regression as described above, for each of the following categories:

- the overall influenza complications
- the pulmonary complications,
- the extrapulmonary complications
- the pulmonary complications including sinusitis and otitis
- the infectious complications
- the non-infectious complications
- the major complications
- the minor complications

Time to resolution of fever

Time to resolution of fever will be analyzed similarly as time to return to daily activities.

A subgroup analysis will be done based on the subset of subjects with fever at baseline (temperature $\geq 37.0^{\circ}\text{C}$) as recorded as part of the on-site vital signs assessment.

Temperature recordings made by the subject on the ePRO device lower than 34°C or higher than 43°C will not be included in the analysis.

5.3.2.4. Viral kinetics

Viral load and viral titer over time

The actual values and change from baseline of the viral load and viral titer over time will be shown descriptively and by mean (SE) plots per analysis timepoint.

Individual AUCs from baseline to Day 10 for both viral load and viral titer will be calculated using the trapezoid method and summarized using descriptive statistics.

Viral load negativity, viral load categorization, and viral titer negativity will be summarized using frequency tabulations (n and %) at each analysis visit.

■ *Difference in mean viral load AUC calculated from baseline to Day 10:*

Post-baseline mean viral load values up to and including Day 10 will be analyzed using a restricted maximum likelihood based repeated measures approach. Analyses will include the fixed, categorical effects of treatment, strata, visit, and treatment-by-visit interaction, as well as the continuous, fixed covariates of baseline viral load and baseline viral load -by-visit interaction. The following list of covariance structures will be applied in the model fit, in the specified order, and the first correlation structure to yield convergence will be applied in the analysis:

- Unstructured [UN]
- Ante-dependence [ANTE(1)]
- Heterogenous Toeplitz [TOEPH]
- Heterogeneous CS [CSH]
- Heterogeneous AR(1) [ARH(1)]
- Toeplitz [TOEP]

The Kenward-Roger approximation will be used to estimate denominator degrees of freedom.

The model above will be used to estimate the difference in the viral AUCs for pimodivir versus placebo.

Post-baseline mean viral titer values up to and including Day 10 will be analyzed as described above for the post-baseline mean viral load values.

A least squares means $\pm 95\%$ CI plot will also be provided for the estimated viral load and estimated viral titer over time.

Time to viral negativity by viral load and by viral titer

The time to viral negativity will be analyzed by Kaplan-Meier analysis, Gehan-Wilcoxon test, log-rank test, AFT model, and Cox proportional hazards model.

The AFT and Cox models will include the fixed categorical effects for treatment (with placebo as the reference) and stratification factors and the baseline viral load, or viral titer, as a continuous variable.

